#### 4.2 Secondary endpoints

Secondary end points are changes in bone mineral density (BMD) at the femoral neck and spine at week 48, the number of patients from both groups maintaining CTX-I and PINP levels within reference range values at week 12, 24 and 48. Reference ranges used will be adjusted according to menopausal status and sex. Percentage changes in BMD and the percentage of patients with a BMD loss higher than the least significant change (LSC), which represents the smallest difference between successive measurements of BMD that can be considered a real change, will be calculated.

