1.5 Hypotheses

It is hypothesized that effervescent alendronate will be able to maintain bone turnover markers within the pre-menopausal reference range thereby reducing the likelihood of bone turnover associated changes, after discontinuation of Prolia treatment in a non-osteoporotic population.

2. Study Objectives and Endpoints

The objectives of the effervescent alendronate treatment after denosumab discontinuation are to investigate if weekly intake of effervescent alendronate can prevent increases in bone turnover above the premenopausal reference range^{*} at week 48 and if there is difference between using alendronate for 24 or 48 weeks, started at the earliest three months but no later than four months after the last injection of denosumab.

Other objectives of the study are:

- to assess the changes in bone turnover after 12 and 24 weeks,
- to explore the impact on dual-energy X-ray absorptiometry (DEXA) parameters after 24 and 48 weeks of treatment
- to assess radiographic changes and investigate if new erosive joints develop at week 24 and 48

The primary endpoint of this objective is the number of patients that maintain C-terminal telopeptide of type I collagen (CTx-I) within the premenopausal reference range at 48 weeks.

Secondary endpoints are the number of patients that maintain CTx-I within the premenopausal reference range at week 12 and 24 as well as the changes in CTx-I and N-terminal propeptide of type I procollagen (P1NP) from baseline until 12, 24 and 48 weeks after randomization to effervescent alendronate.

Co-exploratory objectives are changes in T-score at lumbar spine and hip from baseline to week 24 and week 48, and related to the underlying erosive hand OA disease, the radiographic changes at the finger joints in terms of new (radiographic) erosive joints (n) and GUSS change (Δ) between W24 and W48 and baseline.

Safety-objective

This study will assess the safety of the weekly administration of effervescent alendronate 70mg in the population of patients with erosive OA. Safety evaluations will be made by recording the incidence of AE/SAE

^{*} Reference range: CTX-I (IVD kit) Non menopausal women < 700ng/l. Menopausal women < 730ng/l. Adult male >20 to 120 years: < 695ng/L; P1NP (IVD kit): Male > 45 years: 12.8-71.9 µg/L Non menopausal women: 13.7-71.1 µg/L Menopausal women: < $82.6 \mu g/L$

3. Experimental Plan

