## 2.2 Hypothesis and objectives

It is hypothesized that effervescent alendronate will be able to maintain bone turnover markers within the reference range thereby reducing the likelihood of bone turnover associated changes, after discontinuation of denosumab treatment in a non-osteoporotic population.

The **primary objective** of this study is to assess the effect of effervescent alendronate after denosumab discontinuation on the change in bone turnover markers after 48 weeks in a non-osteoporotic population and to assess if there is a difference between using oral alendronate after 24 or 48 weeks.

The **secondary objective** is to evaluate the effect of effervescent alendronate after denosumab discontinuation on bone mineral density in this non-osteoporotic population and assess difference in oral alendronate therapy for 24 versus 48 weeks.

**Exploratory objectives** are to study the effect of oral alendronate therapy after denosumab discontinuation on erosive destructive progression at the subchondral bone in erosive hand OA patients and to assess the effect of oral alendronate on their hand pain scores.

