#### 2.3 Study design

This is a monocentric randomized study to investigate the effect of effervescent alendronate on bone turnover markers after denosumab discontinuation. At the earliest three months but no later than

four months after the last denosumab injection, 40 subjects will be randomized to effervescent alendronate administered for either 24 (n=20) or 48 weeks (n=20). The randomization was performed by a randomization manager. The total treatment duration per subject is 48 weeks.

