### 3.2.3 Protocol violations and handling of missing data

Major protocol violations thought to affect the assessment of efficacy of the study drug will be considered. The following situations will be considered as major protocol violations:

- Patients who withdrew or were withdrawn from the study
- Patients having received less than 50% of the study medication

Data of withdrawn patients will be included up until the moment of withdrawal. If measurements are recorded after withdrawal when not completed the appropriate duration of active treatment, these measurements will be considered as missing. For analysis of the primary endpoint, all data available will be used for analysis and imputation of missing values will be performed. More specifically, drop-outs will be considered as non-responders in all outcome measures (primary and secondary endpoints where linear mixed models will be used, and in the number of patients exceeding reference ranges). Only in the analyses of percentage changes of BMD and percentage of patients with a BMD loss higher than the least significant change, drop-outs will be considered as true drop-outs.

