#### 5.3 Secondary outcome analysis

Bone density measures will be analysed in an intention to treat approach, using a linear mixed model. Data from all available time points will be used. Normal distribution will be checked and data transformations will be performed if necessary if assumptions of normality are not reached. P-values and estimated marginal means will be calculated at different time points.

In addition, percentage changes in BMD and the percentage of patients with a BMD loss higher than the least significant change (LSC), which represents the smallest difference between successive measurements of BMD that can be considered a real change, will calculated. Here no intention to treat approach will be used.

The number of patients exceeding reference ranges will be calculated with an intention to treat approach, where drop-outs will be considered as non-responders. A Fisher's exact test was used to assess differences in patient numbers exceeding reference ranges between both treatment groups.

All statistical tests were two-tailed and a p-value below 0.05 ( $\alpha$ ) was considered statistically significant.

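### Does it matter that the SAP defines a count of patients within the reference range but tests the number exceeding it?

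*SAP*

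**What the plan says.** Three places in the SAP deal with the reference-range count.

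- SAP 4.2 defines the endpoint as the number of patients in each group "maintaining CTX-I and PINP levels within reference range values at week 12, 24 and 48", and adds: "Reference ranges used will be adjusted according to menopausal status and sex".
- SAP 3.2.3 treats drop-outs as non-responders in the mixed-model outcomes "and in the number of patients exceeding reference ranges".
- SAP 5.3 says: "The number of patients exceeding reference ranges will be calculated with an intention to treat approach". It compares the arms on that number with a two-sided Fisher's exact test at 0.05.

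SAP 4.2 does not print the limits. They stand in the footnote to Protocol section 2:

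| Group | CTX-I (ng/L) | P1NP (µg/L) |
|---|---|---|
| Non-menopausal women | < 700 | 13.7 to 71.1 |
| Menopausal women | < 730 | < 82.6 |
| Men (P1NP limits: over 45 years) | < 695 | 12.8 to 71.9 |

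The hypothesis in Protocol 1.5 is that alendronate will "maintain bone turnover markers within the pre-menopausal reference range". SAP 2.2 has the same hypothesis without the word premenopausal: "maintain bone turnover markers within the reference range thereby reducing the likelihood of bone turnover associated changes". The objective in Protocol section 2 is one-sided: it concerns increases above the range.

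**The concern.** The endpoint that is defined and the endpoint that is tested have different names, and the SAP does not say that one is the complement of the other. If exceeding means above the upper limit, a man over 45 with a P1NP of 10 µg/L fails the count in 4.2 and passes the one in 5.3.

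This could matter by arm. At week 48 the 24-week arm has been off alendronate for about 24 weeks, and the 48-week arm is just finishing. If bone formation is more strongly suppressed in the 48-week arm, a two-sided count adds failures there and offsets failures from rebound in the other arm. With 20 patients per arm, one reclassified patient can move a Fisher p-value across 0.05.

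A second worry is which range applies. The protocol speaks of a premenopausal range, the SAP of ranges by sex and menopausal status.

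**Working it through.** The documents give no event rate, power or sample size calculation for this endpoint (Protocol 11.3), so there is no stated figure to reproduce.

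**Step 1. Where do the two counts disagree?** Call a value *within* if it lies between the printed limits (or below the upper limit where no lower one is printed), and *exceeding* if it lies above the upper limit. Leaving aside exact ties with a limit:

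| Marker and group | Low value (10) | Mid value (40) | Value 20% above the upper limit |
|---|---|---|---|
| CTX-I, all groups | agree | agree | agree |
| P1NP, menopausal women | agree | agree | agree |
| P1NP, men over 45 | **disagree** | agree | agree |
| P1NP, non-menopausal women | **disagree** | agree | agree |

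Only a P1NP below 12.8 or 13.7 µg/L is affected. Protocol 5.1 expects premenopausal women to be a very small minority, so in practice this concerns men, whose number is not given.

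**Step 2. How many patients?** All inputs here are assumptions: log-normal P1NP with log-SD 0.4 to 0.5, and 2 to 6 men per arm. The proportion below the male limit is Φ(ln(12.8/median)/log-SD).

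| Assumed median (µg/L) | Log-SD 0.4 | Log-SD 0.5 | Expected men below 12.8, per arm |
|---|---|---|---|
| 20 | Φ(−1.116) = 0.132 | Φ(−0.893) = 0.186 | 2 × 0.132 = 0.26 to 6 × 0.186 = 1.12 |
| 35 | Φ(−2.515) = 0.006 | Φ(−2.012) = 0.022 | 2 × 0.006 = 0.01 to 6 × 0.022 = 0.13 |
| 60 | Φ(−3.862) = 0.0001 | Φ(−3.090) = 0.001 | below 0.01 |

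The discrepancy is therefore about 0 to 1 patient in an arm, and it gets near 1 only with strong suppression and several men. Both arms receive the same treatment up to week 24, so a systematic difference between arms is not expected at weeks 12 or 24. It can arise only at week 48.

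**Step 3. What could one patient do to the test?** Assumed counts, 20 per arm, two-sided Fisher's exact test:

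| Above upper limit, 24-week v 48-week arm | p, exceeding | p, not within, after one low P1NP in the 48-week arm |
|---|---|---|
| 6 v 0 | 0.020 | 0.091 |
| 8 v 1 | 0.020 | 0.065 |
| 10 v 3 | 0.041 | 0.096 |

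These counts were chosen near the threshold, so they show what is possible, not what is likely.

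**Step 4. Which count does the plan test?** SAP 5.3 attaches Fisher's test to the number exceeding, and the drop-out rule in 3.2.3 uses the same word. The protocol objective looks upward only. The left-hand p-values in Step 3 are the ones the plan produces as written, and harmonised wording based on the upper limit would produce the same ones.

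**Step 5. Which range?** In Protocol section 2 the phrase about the premenopausal range carries an asterisk, and the footnote it points to lists all three groups. The SAP's use of limits by sex and menopausal status follows that footnote. If 700 ng/L were nevertheless applied to menopausal women in place of 730, the proportion between the two limits is 0.4% (assumed median 300, log-SD 0.4) to 3.8% (median 600, log-SD 0.4). That is at most 40 × 0.038 = 1.5 patients, even if all 40 were menopausal women.

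**The case for a change.** The best argument for acting is that this is an open-label trial with small arms, that one patient can decide a Fisher test, and that an undefined term leaves a choice that could be made after the results are known. Aligning the wording would cost a few words and no data.

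Part of this stands. The wording does differ, the SAP never says how a P1NP below the lower limit is classified, and 4.2 does not cite the footnote for its limits. A table built from 4.2 alone could come out slightly different from the one tested under 5.3.

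The argument weakens at the point of choice. The tested variable is not left open: 5.3 names it, 3.2.3 uses the same term, and the protocol's direction supports it. An analyst would have to depart from 5.3 to test anything else. One could also read exceeding loosely, as outside on either side. Then 4.2 and 5.3 agree, though the test would also count low values, which fits the protocol objective less well. A two-sided P1NP count is defensible in its own right, so the case for ruling it out is not strong.

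**Conclusion.** The inconsistency is real but clerical, and no change to the plan is needed. It is confined to P1NP below a lower limit in men over 45 and in the few non-menopausal women, within a secondary endpoint of the SAP. The SAP's primary mixed model, every CTX-I count (including the protocol's primary endpoint) and all menopausal women give the same result under either word. Where the words do differ, 5.3 already tests the count that fits the protocol's aim.

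On the assumed inputs (2 to 6 men per arm, P1NP medians of 20 to 60 µg/L, log-SD 0.4 to 0.5) the gap at week 48 is about 0 to 1 patient in the 48-week arm. That size rests wholly on assumptions, because the documents give neither the number of men nor any P1NP distribution. The conclusion depends less on the size than on reading exceeding in its ordinary sense, above the upper limit. The question of which range applies is at most a missing cross-reference, since the protocol's own footnote gives limits by sex and menopausal status.

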#### 4.3 Safety data

Analysis of the safety data set will be performed. This will include the occurrence on incidence and severity of adverse events and serious adverse events. These will be categorized according to the involved organ systems. The number of the events will be reported and compared between both treatment groups. Changes in routine clinical laboratory tests (calcium, vitamin D, creatinine, urine and GFR) will also be analyses

#### 4.3 Exploratory outcomes measures

Exploratory end points are the development of new erosive joints (using the Verbruggen and Veys anatomical phase scoring system) (2) and hand pain scores, measured using a NRS pain scale at week 48.

### 5. Statistical analysis

All statistical analyses will be performed using R and RStudio (version 4.1.1).

All continuous variable will summarized using mean and standard deviation (SD). Frequency count and percentages will be used to summarise categorical variables.

### 5.1 Summary of baseline data

A brief summary of descriptive statistics will be provided including demographic features and disease specific characteristics. Demographic baseline data will be compared between both treatment groups.

### 5.2 Primary outcome analysis

The primary outcome analysis will be performed in an intention to treat approach, where drop-outs were considered as non-responders. Changes in bone turnover marker levels will be analysed with a linear mixed model. Data from all available time points will be used. Normal distribution will be checked and data transformations will be performed if necessary if assumptions of normality aren't reached. P-values and estimated marginal means will be calculated at different time points.

All analyses will be performed with a two-sided p-value. A p-value below 0.05 (p<0.05) will be considered statistically significant.

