Main Endpoints	 The primary endpoint of this objective is to assess the number of patients that maintain C-terminal telopeptide of type I collagen (CTx-I) levels within the premenopausal reference range at 48 weeks. Secondary endpoints are the assessment of the number of patients that maintain CTx-I levels within the premenopausal reference range at week 12 and 24 as well as the changes in CTx-I and N-terminal propeptide of type I procollagen (P1NP) levels from baseline until 12, 24 and 48 weeks after randomization to effervescent alendronate. Co-exploratory objectives are changes in T-score at lumbar spine and hip from baseline to week 24 and week 48, and the radiographic changes at the finger joints in terms of new erosive joints and GUSS change between W24 and W48 and baseline. 				
Hypothesis	The main hypothesis is that effervescent alendronate will be able to maintain bone turnover markers within the pre-menopausal reference range, thereby reducing the likelihood of bone turnover associated changes.				
Study Sites	1 site – the UZ Ghent site				
Subjects	40 subjects for the alendronate follow-up study				
Enrolment	72 weeks				
Main Eligibility Criteria	Subject must have completed our three year study 'RANKL-blockade for the treatment of erosive osteoarthritis (OA) of interphalangeal finger joints' (EudraCT number: 2015-003223-53; Protocolnumber: AGO/2015/008)				
Study treatment Duration	48 weeks				

Table of Contents

- Protocol Title and Investigators
- Protocol signature page
- Protocol synopsis

1. Background and Rationale

- 1.1 Disease background
- 1.2 Denosumab
- 1.3 Effervescent alendronate
- 1.4 Rationale for study design
- 1.5 Hypotheses

2. Study Objectives and Endpoints

3. Experimental Plan

- 3.1 Study design and schematic
- 3.2 Number of sites
- 3.3 Number of subjects
- 3.4 Estimated study duration
- 3.5 Subject Eligibility
 - 3.5.1 Inclusion criteria
 - 3.5.2 Exclusion criteria
- 3.6 Criteria for withdrawal

4. Medication

- 4.1 Composition and dosing
- 4.2 Producer
- 4.3 Distributor
- 4.4 Packaging
- 4.5 Administration way
- 4.6 Labelling:
- 4.7 Storage conditions:
- 4.8 Known side effects of the medication
- 4.9 Drug accountability

5. Procedures

- 5.1 Study procedures
- 5.2 Study table
- 5.3 Sample processing

6. Randomisation

7. Reporting requirements for investigational product complaints

- 8. Concomitant therapy
- 9. End of study
- 10. Adverse Events/Adverse Event reporting
 - 10.1. Definitions

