11.1 Efficacy analysis

Complete and specific details of the final statistical analysis will be described and fully documented in the Statistical Analysis Plan (SAP). The SAP will be finalized prior to the database lock. The analysis will be performed using the statistical software package IBM SPSS. Demographic and baseline characteristics will be summarized. The number of observations, mean, standard deviation, median, minimum and maximum will be summarized for continuous variables. Discrete variables will be summarized by counts and percentages.

Primary analysis will be a per protocol approach, including all patients who completed the final visit (week 48). Missing data related to exploratory endpoints will be handled by last observation carried forward (LOCF) procedure.

The primary efficacy variables will be the number of patients that maintain CTx-I within the premenopausal reference range at week 48. Secondary efficacy variables will be the changes from baseline to week 12, 24 and 48 for CTx-I and P1NP levels. Co-exploratory variables will be DXA changes from baseline to week 24 and 48. Hand OA-related exploratory efficacy variables will be changes in NRS pain from baseline to week 12, 24 and 48, and changes in number of new erosive joints on X-rays and changes in GUSS values from baseline to W24 and 48.

All analyses be summarized by treatment group where treatment group equals 'exposed to Alendronate for 48 weeks Vs Alendronate for 24 weeks'.

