## 4. Outcome measures

#### 4.1 Primary endpoints

The primary end point of this study is to investigate if effervescent alendronate is able to maintain bone turnover markers after discontinuation of denosumab in a non-osteoporotic population. The outcome measures being used for this are the bone turnover markers CTX-I (C-terminal telopeptide of type I collagen) a marker that reflects the breakdown of bone and PINP (N-terminal propeptide of type I collagen) a marker that reflects the formation of new bone. The primary end point will be the difference in these bone turnover markers after 48 weeks between both treatment arms.

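### The SAP makes both CTX-I and P1NP at week 48 primary without an either/both rule, so the primary conclusion is ambiguous if only one marker is significant

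*SAP*

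**What the plan says.** SAP 4.1 introduces two markers. The first comes with "The outcome measures being used for this are the bone turnover markers CTX-I". The second is P1NP (printed as PINP), described as "a marker that reflects the formation of new bone". It then defines one endpoint over the pair: "The primary end point will be the difference in these bone turnover markers after 48 weeks between both treatment arms".

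SAP 5.2 analyses the marker levels with a linear mixed model using all time points. On testing it says "All analyses will be performed with a two-sided p-value", followed by "A p-value below 0.05 (p<0.05) will be considered statistically significant".

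The protocol is different. Its synopsis counts patients who keep CTx-I "levels within the premenopausal reference range at 48 weeks", and section 11.1 repeats this: "The primary efficacy variables will be the number of patients that maintain CTx-I within the premenopausal reference range at week 48". Continuous changes rank lower there: "Secondary efficacy variables will be the changes from baseline to week 12, 24 and 48 for CTx-I and P1NP levels". In SAP 4.2 the in-range counts, for both markers, are secondary.

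No either/both rule, testing order, composite or alpha split appears in SAP sections 2 to 6 or in protocol section 11. SAP section 1 (study identification) was not in the text available, but the SAP contents list shows no section on multiplicity or decision rules.

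**The concern.** The time point is settled: week 48. What is missing is the rule that turns two p-values into one primary conclusion. If CTX-I is below 0.05 and P1NP is not, or the reverse, one reader of SAP 4.1 and 5.2 could report a positive primary result and another a negative one. Each could cite the same text.

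Two things are at stake. The rule could be picked once the p-values are known. And if either marker is then accepted as sufficient, the primary claim carries more than the 5% error that the threshold implies.

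**Working it through.** The plan has no derived figure to reproduce: protocol 11.3 reports that no sample size calculation was made, and 0.05 is simply a stated threshold.

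**Inputs from the documents.** Two primary markers (SAP 4.1); two-sided 0.05 for each test (SAP 5.2); 20 patients per arm (SAP 2.3, protocol 3.1).

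**Assumptions.** The documents give neither the correlation between the two test statistics nor an effect size. Correlation is varied from 0 to 0.9. Standardised effects at week 48 are 0.5, 0.91 and 1.5 SD on both markers, and 0.91 SD on one with 0.5 SD on the other. There is no dropout, and each marker is compared by a two-sample t-test.

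**Step 1: no true difference on either marker.**

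P(either) = 0.05 + 0.05 − P(both), and P(exactly one) = P(either) − P(both).

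At correlation 0, P(both) = 0.05² = 0.0025, so P(either) = 0.10 − 0.0025 = 0.0975 and P(exactly one) = 0.0975 − 0.0025 = 0.0950. For the other rows, P(both) comes from the bivariate normal distribution.

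| Correlation | Both significant | Either significant | Exactly one |
|---|---|---|---|
| 0 | 0.25% | 9.75% | 9.5% |
| 0.5 | 0.93% | 9.07% | 8.1% |
| 0.7 | 1.65% | 8.35% | 6.7% |
| 0.9 | 2.96% | 7.04% | 4.1% |

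- *Either marker enough:* the rate is 7.0% to 9.75% over this range. It falls to 5% only as the correlation approaches 1 (6.5% at 0.95, 5.7% at 0.99).
- *Both required:* the least favourable case is one marker with a large true difference and the other with none. Simulation with 3 SD on one marker and 0 on the other gives 5.0% at every correlation, so the bound is 5%.
- *Either marker enough at 0.025 each:* 1 − 0.975² = 4.9% at correlation 0, and 3.6% at 0.9.

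**Step 2: power of one test.** The non-centrality is d × √(20/2), with 38 degrees of freedom. For d = 0.909 it is 0.909 × 3.162 = 2.87, which gives 80% power at 0.05 and 70% at 0.025. For d = 0.5 it is 1.58, giving 33.8% at 0.05. For d = 1.5 it is 4.74, giving 99.6%.

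**Step 3: chance of a split when there are true differences.** At correlation 0 this is p₁(1 − p₂) + p₂(1 − p₁):

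- 0.5 SD on both: 2 × 0.338 × 0.662 = 45%
- 0.91 SD on both: 2 × 0.80 × 0.20 = 32%
- 1.5 SD on both: 2 × 0.996 × 0.004 = 0.8%
- 0.91 and 0.5 SD: 0.80 × 0.662 + 0.338 × 0.20 = 60%

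Simulated t-tests extend this to correlation 0.9:

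| Assumed effect (SD) | Split at correlation 0 | Split at correlation 0.9 |
|---|---|---|
| 0.5 on both | 45% | 13% |
| 0.91 on both | 32% | 10% |
| 1.5 on both | under 1% | under 1% |
| 0.91 and 0.5 | 60% | 46% |

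**Step 4: power if both are required.** At 0.91 SD on each marker it is 64%, 69%, 71% and 75% at correlations 0, 0.5, 0.7 and 0.9, against 80% for a single test.

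**The case against.** The strongest reply is that the SAP names one endpoint over both markers, in the singular, and can fairly be read as requiring both. A split would then mean that the primary was not met, with error at most 5%. This reading is available, so calling the conclusion wholly undefined would go too far. But the SAP does not state it, and it carries a power cost that the SAP does not mention.

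Several stronger readings are tempting and are not supported:

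- *That the plan as written has a false-positive rate near 10%.* Naming two primary markers does not by itself inflate error. That needs an either-marker rule, and the SAP never adopts one.
- *That a split is likely.* The chance runs from under 1% to about 60% across assumed effects that no document supplies.
- *That the protocol already ranks CTX-I first for this analysis.* CTX-I is its only primary marker, but as an in-range count. As continuous changes, CTX-I and P1NP are both secondary.
- *That the SAP was written after results were known.* Section 5.3 slips into the past tense, and the reference list has an item dated 2024, while section 6 places data lock after June 2022. The date of the SAP is not in the text available, so this is not shown. It does mean that the remedy needs a timing condition.

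It is also fair that this is a single-centre, open-label trial of 40 patients, with size set by availability. That limits the weight of the point. A formal significance threshold on a primary outcome still needs a rule.

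**Conclusion.** The concern stands as an ambiguity in the primary decision rule that should be resolved. The absence of a rule is plain from the text and rests on no assumption.

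Its consequences are conditional. The 7.0% to 9.75% error rate applies only if either marker is taken as enough, and depends on the assumed correlation. The both-required reading holds error to 5% or less, at the price of power. The split and power figures rest on assumed effects, 20 per arm, no dropout and simple t-tests. The planned mixed model, with drop-outs counted as non-responders, will give different values.

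**What to change.** In SAP 4.1 and 5.2, name the between-arm difference in CTX-I at week 48 as the single primary test at two-sided 0.05. Test P1NP at week 48 only if CTX-I is significant. This is a preference among valid rules; its support is that CTX-I is the protocol's only primary marker.

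**Cost.** For the marker rule alone this is a change of SAP wording. CTX-I keeps its full power. P1NP can no longer be claimed as a primary result on its own, and its gated power is the joint figure (64% to 75% in the 0.91 SD case). Requiring both markers has that same power for the whole primary claim. Testing each at 0.025 gives about 70% per marker. Either alternative controls error, provided that the SAP names it.

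**Reconcile the endpoint.** The SAP must also reconcile its continuous primary with the protocol's count of patients in range, and give the reason. If the continuous form is kept, this is more than wording, because it departs from the protocol's primary endpoint.

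**Timing.** Fix the rule before any between-arm results are seen. If they have been seen, label the change post hoc and report both markers under a conservative reading (both required, or 0.025 each).
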